Enrollment will be done prospectively until the desired number of patients is reached. This study is planned as a parallel group randomized trial. One group of patients will be randomized to SIM plus PEG while the other group will be randomized to PEG only. The dose of SIM that will be used in this study is 480 mg (2-times higher than the dose used in previous studies). The rationale for using a high dose is to maximize our outcome yield. Our proposed sample size is 300 patients. In our unit, we perform approximately 60 screening colonoscopies per week. We anticipate that approximately 10% of these patients will be eligible to participate in the study. Therefore, we expect to enroll the desired number of patients in approximately 24 months.

Data Collection:

For each patient, the following data will be collected:

1. Age (years)
2. Gender (male/female)
3. Ethnicity (Hispanics/non-Hispanics)
4. Past medical and surgical history (yes/no)
5. Bowel preparation quality (poor, fair, good, very good, excellent)
6. Boston preparation scale score
7. Bubble scale score
8. Cecal intubation time (minutes and seconds)
9. Withdrawal time (minutes and seconds)
10. Effective procedure time (minutes and seconds)
11. Number and size of polyps detected
12. Number of adenomas detected

13. Intra-procedure use of SIM

Sample size calculation

The dose of simethicone that will be used in this study is 480 mg (2-times higher than the dose used in previous studies). The rationale for using a high dose is to maximize our outcome yield. Our sample size calculation was based on articles by Yoo et al⁸, Jansen et al⁹ and Bai et al¹⁰ using the following formula considering ADR as the primary outcome:

$$n = 2 \frac{\left(z_{1-\frac{\alpha}{2}} + z_{1-\beta} \right)^2 pq}{(p_1 - p_2)^2}$$

Where p1 was the % of outcome in the intervention group and p2 the % of outcome in the control group. Bai et al¹⁰ reported ADR of 21.0% in the PEG+SIM group and 14.3% in the PEG group. With these results, a sample size of 509 per group would be suitable for the parent study. For the pilot study, 10% of the calculated sample size for the parent study would be an acceptable estimation¹³. Considering the heterogeneity of the study by Bai et al, we decided to include 20% of the total calculated sample size in this pilot study. Therefore, 102 patients per group would be an appropriate sample size to compare ADR in this pilot study.

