Other outcomes to explore in the current study include preparation quality and PDR. Yoo et al⁸ reported that 99% of patients receiving PEG+SIM had BPS scores of 6-9 compared to only 84% in the patients who received PEG. Considering BPS scores as the outcome (p1=99% and q1=84%), with $\alpha=0.05$ and $\beta=0.2$, a total of 110 patients will be needed, 55 in each arm. On the other hand, Jansen et al⁹ reported that PDR in patients who received PEG+SIM was 26.7% compared to 13.7% in those who received PEG. With these results and following the same formula, a sample size of 150 patients per group will be needed to evaluate both bowel preparation and PDR. Therefore, in order to have a sufficient study power and examine all parameters (ADR, PDR and bowel preparation quality), we decided to include 150 patients per group for a total of 300 patients.

Statistical analysis

1. Continuous data (e.g. effective procedure time, withdrawal time) will be described using mean and standard deviation (SD) or Median (Q1, Q3) based on D'Agostino-Pearson normality test in each group and will be compared with either independent t-test or nonparametric Mann-Whitney. Interval data (e.g. BPS, BS) will be presented as Median (Q1, Q3) in each group and compared with nonparametric Mann-Whitney. Categorical data (e.g. ADR) will be described using frequency and proportion (%) in each group and will be compared using Chi-square or Fisher's exact test where appropriate. Further, number needed to treat (NNT) using SIM+PEG will be determined. Cohen's kappa coefficient will be used to measure inter-rater agreement between two endoscopists who will score BS and BPS. In the eventual presence of baseline differences in cofactors, a relative risk regression developed by our biostatistician¹⁴ will be used

to determine adjusted effect of SIM+PEG compared to PEG alone on PDR and ADR. Other findings at colonoscopy

All the statistical analyses will be performed using STATA 14 and p-values less than 5% will be considered significant results. All the statistical analyses will be performed by our Biostatistics and Epidemiology Consulting Lab (BECL) under the supervision of [name].

METHODS

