Patients will be included in the study in a prospective manner at University Medical Center of El Paso endoscopy unit. At the time of the pre-op appointment, the assessment nurse will provide all patients with routine instructions for colonoscopy including diet, hydration and fasting. At the same appointment, the research coordinator, and/or an investigator will consent the patients and the research coordinator will randomize them using a random number list generated by a simple block randomization scheme by our study statistician, to one of two possible preparations: PEG+ SIM or PEG alone. The randomization will be via sealed envelopes that will contain cards with the type of preparation to be used. These coded envelopes will be randomly chosen by the patient. Following randomization each patient will be assigned a code corresponding to one of the two preparation regimens. This code will be noted and placed in a master spreadsheet that only the study coordinator and/or assigned research personnel will handle. The simethicone and instructions will be provided to the patients by the research coordinator. Patients randomized to PEG+SIM will drink 2L of PEG at 5 PM the evening before colonoscopy, and 2L 4hrs prior to the colonoscopy. Patients in this group will be instructed to fill a standard 0.6 ml dropper with SIM suspension (40 mg/0.6 ml) a total of 12 times and add it to the gallon of PEG solution. Patients assigned to PEG will drink the preparation in the exact same manner but without SIM.

Prior to the procedure, a safety assessment of each patient will be completed which will include vital signs and a general examination. Patients will also complete a questionnaire evaluating compliance and side effects from the preparation. This questionnaire will be administered and collected by an assigned research team member. The patients will be instructed not to disclose any information regarding the preparation regimen to the endoscopist or any of the procedure nurses.

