Colonoscopies will be performed by 4 experienced endoscopists who will be blind to the type of preparation the patient received. All procedures will be performed using Olympus 190 colonoscopes. During colonoscopy, standard parameters such as cecal intubation time, withdrawal time and number of polyps detected will be recorded. For the purpose of this study, withdrawal time will be measured as follows: the timer will be started upon initiation of endoscope withdrawal once the cecum has been reached, and it will be paused every time the endoscopist needs to perform any maneuver or intervention such as polypectomy, biopsy, clip placement, hemostasis, suction for >5 seconds etc. Once the endoscopist is done performing any of these, the timer will be re-started. Endoscopists will be free to ask for SIM during the procedure if he/she deems it necessary and the amount will be recorded by the research coordinator. In addition, endoscopists will be asked to score the preparation according to

the standardized BS (0-3; 3 being the worst) and the BPS (3-0; 3 being the best) . A total BPS score of >6 and a BS of <2 will be considered adequate preparations.

The BS that will be used in this study is the one previously used by Sudduth et al (7). This score grades different sections of the colon as follows: 0 = no or minimal, scattered bubbles believed not to be interfering with the examination; 1 = bubbles covering at least half the luminal diameter; 2 = bubbles covering the circumference of the lumen; 3 = bubbles filling the entire lumen. The overall BS and BPS scores will be determined by adding the scores of each segment of the colon (rectosigmoid, transverse and ascending). For example, in a patient whose individual segment BS scores are as follows: 0,2,1; the final score is 3. All endoscopists will be trained in the use of both scales prior to their participation in the study. The bubble scale and the BPS scores will be independently determined by the endoscopist performing the procedure and by a second endoscopist who will review the still previously selected and labeled by the performing endoscopist and will assign his own score based on these images. Each endoscopist will be blind to the score provided by the other one and inter-observer agreement will be calculated.

The ADR will be calculated once the pathology results of the polyps removed become available.

INNOVATIONS

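### The performing endoscopist (one of four) is neither a listed data item nor an analysis term: a minor loss of precision that is cheap to repair

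*Combined protocol and SAP*

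**What the plan says.** METHODS puts every procedure in the hands of four operators: "Colonoscopies will be performed by 4 experienced endoscopists who will be blind to the type of preparation the patient received". At the procedure, "standard parameters such as cecal intubation time, withdrawal time and number of polyps detected will be recorded"; the operator's identity is not among the examples given. Data Collection opens with "For each patient, the following data will be collected" and lists 13 items. The performing endoscopist is not one of them.

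Allocation uses "a random number list generated by a simple block randomization scheme by our study statistician", with no stratification factor named.

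Under Statistical analysis, ADR is summarised as a proportion by arm, and the arms "will be compared using Chi-square or Fisher's exact test where appropriate". Continuous outcomes, including withdrawal time, get a t-test or Mann-Whitney test. An adjusted analysis is foreseen for ADR and PDR only, and only conditionally: "In the eventual presence of baseline differences in cofactors, a relative risk regression developed by our biostatistician". No cofactor is listed. Endoscopists enter the analysis in one place, as raters: "Cohen's kappa coefficient will be used to measure inter-rater agreement between two endoscopists who will score BS and BPS".

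**The concern.** The endoscopist produces or decides ADR, PDR, withdrawal time, intra-procedure simethicone use (left to the operator's discretion in METHODS) and both preparation scores. BACKGROUND/SIGNIFICANCE itself treats ADR as a quality measure for colonoscopy. If the four operators differ, that variation stays in the residual of every comparison between arms, although it could be removed at little cost.

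The conditional regression is a weak safeguard. It depends on a difference being observed, names no covariates, and does not extend to withdrawal time, simethicone use or the preparation scores.

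INNOVATIONS says that the pilot's data will be used to design a full-sized trial. Between-operator spread is an input to that design, and the pilot can supply it only if operator is kept as a study variable.

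**Working it through.** **Inputs from the documents.** Four operators (METHODS); ADR 21.0% vs 14.3% (Sample size calculation); PDR 26.7% vs 13.7%, α = 0.05, β = 0.2 and 150 per group (paragraphs that follow). The α and β are stated for the BPS calculation and taken here as common to all three.

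**Inputs assumed.** The between-operator spread, since the documents give none; several values are shown.

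**1. The plan's own figures.** From n = 2(z₁₋α/₂ + z₁₋β)² p̄q̄/(p₁ − p₂)², with (1.960 + 0.842)² = 7.849:
- ADR: p̄ = 0.1765, so n = 2 × 7.849 × 0.1765 × 0.8235 / 0.067² = 508.3, rounded up to 509, as stated.
- PDR: p̄ = 0.202, so n = 2 × 7.849 × 0.202 × 0.798 / 0.130² = 149.7, rounded up to 150, as stated.

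At 150 per group, power is 33% for ADR and 80% for PDR. The sampling SE of the ADR difference is √[(0.21 × 0.79 + 0.143 × 0.857)/150] = 4.4 points.

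**2. How far chance operator mix moves the ADR difference.** Let σ² be the variance of the operators' ADRs, with equal caseloads. The SD of the shift is √(2σ²/n).
- Assume operator ADRs of 10, 14, 20 and 28%. The mean is 18 and σ² = (64 + 16 + 4 + 100)/4 = 46 squared points.
- SD = √(2 × 46/150) = 0.78 points. The shift exceeds 1 point in about 20% of trials.
- This is not added to the sampling error; it is part of it. The binomial variance at 18% is 18 × 82 = 1476, of which 46 (3.1%) lies between operators.
- The null SE is √(2 × 1476/150) = 4.44 points. Removing the operator component gives √(2 × 1430/150) = 4.37 points.

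**3. Type I error and ADR power.** Simulation of 40,000 trials per row: 150 per arm, four operators with equal caseloads, randomization not stratified by operator, 21.0% vs 14.3% as a constant risk ratio. Pearson chi-square is compared with the Cochran-Mantel-Haenszel (CMH) test stratified by endoscopist.

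| Assumed control ADRs by operator (%) | Variance share | SD of shift (points) | Power, chi-square | Power, CMH | Change (points) |
|---|---|---|---|---|---|
| 14.3 for all | 0% | 0 | 33.2% | 32.6% | −0.6 |
| 10, 13, 15.6, 18.6 | 0.8% | 0.4 | 32.8% | 32.9% | +0.1 |
| 7, 12, 16.6, 21.6 | 2.4% | 0.6 | 32.9% | 33.2% | +0.3 |
| 5, 10, 17.2, 25 | 4.6% | 0.9 | 33.1% | 34.4% | +1.3 |

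With caseloads of 40/30/20/10% the changes are −0.3, +0.1, +0.5 and +1.0 points. With no true effect, the chi-square test rejected in 4.9% to 5.2% of trials across all these settings. As a sensitivity case outside the plan's rates (control ADR 25%, difference 10 points), an operator spread of 10 to 40% gave a gain of 1.7 points (47.5% to 49.2%).

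**4. PDR.** With operator PDRs of 7, 11, 16 and 20.8%, power goes from 81.1% to 82.0%. With no spread it goes from 81.2% to 80.6%.

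**5. Continuous outcomes.** If operators explain a share r of the variance, adjustment divides the SE by 1/√(1 − r), so power = Φ(2.802/√(1 − r) − 1.960) for a comparison that starts at 80%.
- r = 5%: Φ(0.914) = 82%.
- r = 10%: Φ(0.993) = 84%.
- r = 20%: Φ(1.172) = 88%, equivalent to 1/0.8 = 1.25 times the patients.

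The 80% starting point is illustrative, because the plan states no power for withdrawal time or simethicone use. The normal approximation is rougher for simethicone use if many patients receive none.

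**The case against.** A reader might infer that the crude comparison mistakes operator mix for a treatment effect. The documents do not support that. Allocation is randomized and operators are blinded, so the mix differs between arms only by chance, and the variance used by the planned test already contains that chance. With the 10/14/20/28% spread and no true effect, 200,000 simulated trials gave a type I error of 4.96%.

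A reader might also infer that the conditional regression could not include the operator. The plan speaks of cofactors without restricting them to patient characteristics, so operator is not excluded. It is simply not named, and the adjustment remains conditional.

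Nor does absence from the list prove that the operator goes unrecorded. Vital signs, the compliance questionnaire and the allocation code are also collected without being listed. The eligibility criteria depend on who performs the procedure, and a second endoscopist must score the first one's images.

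The design already limits operator variation: experienced attending gastroenterologists, no fellows, one colonoscope series and training in both scales.

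All of this stands, and it reduces the point to precision and reporting. It does not remove the point. Operator is still unnamed in the data list and in every comparison between arms, and the outcomes outside ADR and PDR have no adjusted analysis.

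**Conclusion.** The point holds as a minor one about precision. For ADR, stratifying by endoscopist is worth about 1 point of power at the plan's own rates, and slightly less than nothing if operators do not differ. The 33% ADR power comes from the sample size, not from this omission, and a reader should not connect the two. The better case rests on withdrawal time and simethicone use, where the gain could be 2 to 8 points from an 80% start, and on the information the full trial will need.

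These sizes rest on assumed operator spreads and variance shares, and on patients reaching operators independently of arm, which blinding supports.

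**What to change.** 1. Add a coded endoscopist field (1–4) to Data Collection.
2. Prespecify, regardless of observed imbalance, an endoscopist-stratified comparison of ADR and PDR: either Mantel-Haenszel, or the plan's relative risk regression with endoscopist as a fixed factor. Four levels are too few for a reliable random effect.
3. For withdrawal time and simethicone use, replace the plain t-test or Mann-Whitney test with a linear model containing endoscopist or a van Elteren test stratified by endoscopist.
4. Report ADR by endoscopist, to inform the full trial.

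Stratified randomization is not needed. It would also require the operator to be known at the pre-op appointment, which the documents do not state.

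The cost is one data field, three degrees of freedom among 300 patients, and a negligible power loss if operators do not differ. It does change the stated primary and secondary tests, so it should be written into the plan before the data are analysed. Treatment, allocation and sample size are unaffected.

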An adequate bowel preparation is paramount for a screening colonoscopy. Mucosal visualization can be dramatically affected by residual stool, bubbles, bile, intraluminal fluid or debris (1, 2). Any of these features can ultimately lead to missed lesions, prolonged endoscopy duration, and decreased patient tolerance. PEG is one of the most commonly used CPAs. A few studies have reported that the addition of low to medium doses of SIM to lower volume PEG regimens (2L) or other CPAs such as sodium phosphate results in overall better colon preparations based on a standardized bubble scale (BS) and Boston preparation scales (BPS) (3-9). Some of these studies have also reported a trend towards a higher number of polyps detected in the patients who added SIM to their CPA. This finding did not reach statistical significance likely due to the fact that they were neither powered enough nor primarily designed to do so.

It is important however, to understand that SIM is not a CPA. It is an anti-foam medication and its purpose is to decrease the amount of bubbles interfering with visualization, provided that there is no stool present. In clinical practice, it is very common to use it as a flush through the endoscope at the time of the procedure for that purpose. Nevertheless, such use of SIM has been recently associated with the formation of biofilm inside the endoscope's operative channels that is not eliminated by standard disinfecting and reprocessing techniques (10). This biofilm leads to persistent moisture that has been noted as a contributing factor to outbreaks of multi-drug resistant microorganisms in a few high level endoscopy centers (11).

In summary, previous studies have shown a trend towards a better overall preparation, and a higher polyp detection rate when a low to medium dose of SIM is added to a CPA. Therefore, the present pilot study is designed to determine if adding high dose SIM to a regular 4L PEG has the potential to positively impact the ADR, a benchmark quality indicator of screening colonoscopy. Adding a high dose SIM to a CPA could not only result in a higher ADR, but also in a decrease use of SIM through the endoscope at the time of the procedure, reducing the risk of possible life threatening infections for future patients.

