The intervention in this study although simple and inexpensive has the potential of making a significant impact in the health of our already underserved population. Our health sciences center is the only academic medical facility performing clinical and basic science research in southwest Texas and we serve a large number of patients, most of which are Hispanic Americans with only limited access to healthcare.

RESEARCH PLAN

Study Design:

This is a single-center, prospective, randomized controlled, observer-blinded study of patients undergoing screening colonoscopy at a tertiary care medical facility.

Primary endpoint

To establish if the ADR improves with the addition of high dose SIM suspension to a polyethylene glycol (PEG) preparation

Secondary endpoints

1. Determine if adding a high dose of SIM to PEG reduces the withdrawal times during the screening colonoscopy.
2. Determine if adding a high dose of SIM to PEG results in an overall better colon preparation.
3. Determine if adding a high dose of SIM to PEG results in less intra-procedural use of SIM.
4. Determine if adding a high dose of SIM to PEG results in a higher polyp detection rate

Inclusion criteria:

1. Patients between the ages of 30-75 scheduled for screening colonoscopy.
2. Male and female patients

3. Ambulatory patients
4. Signed informed consent form
5. Colonoscopy performed by an attending gastroenterologist
6. The use of both Moderate Sedation and Monitored Anesthesia Care (MAC) sedation

Exclusion criteria:

1. Previous colonic surgery
2. Patient with mental/physical condition that impairs oral ingestion of preparation
3. Allergy or hypersensitivity to simethicone
4. Patients with limited mobility (bedridden patients)
5. Patients with gastrointestinal obstruction
6. Patients with GI motility disorders(e.g. achalasia, gastroparesis, chronic constipation)
7. Colonoscopy performed by GI fellows

Patient Enrollment:

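### Intra-procedure simethicone use (secondary endpoint 3) is recorded by the same role that randomises patients and hands out the simethicone; naming a blinded recorder would be a minor, cheap improvement

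*Combined protocol and SAP*

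**What the plan says.** The Study Design section describes the trial in these terms: "This is a single-center, prospective, randomized controlled, observer-blinded study". The third secondary endpoint is: "Determine if adding a high dose of SIM to PEG results in less intra-procedural use of SIM". The Data Collection list has a matching item, "Intra-procedure use of SIM", and names no recorder for it.

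The Methods section is the only place that names one. Endoscopists may ask for SIM during the procedure, and "the amount will be recorded by the research coordinator".

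Earlier in the Methods, the same role has two tasks tied to the allocation:

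- Randomisation: "the research coordinator will randomize them using a random number list".
- Supply: "The simethicone and instructions will be provided to the patients by the research coordinator".

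On the regimen code, the Methods say: "This code will be noted and placed in a master spreadsheet that only the study coordinator and/or assigned research personnel will handle".

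Blinding to the preparation is stated for the endoscopists who perform the colonoscopies. Patients are told not to reveal their regimen to the endoscopist or the procedure nurses. Neither statement covers the research coordinator.

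**The concern.** Only the PEG+SIM arm receives simethicone before the procedure. Whoever hands it out knows the arm of each patient who gets it, and by elimination the arm of each patient who does not. If that person also writes down how much SIM was used during the colonoscopy, the record of a between-arm endpoint is made with knowledge of the arm. An amount could be missed, rounded or entered late, and not equally in the two arms.

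The endpoint has a purpose of its own. Background/Significance names two possible benefits of the intervention: a higher ADR, "but also in a decrease use of SIM through the endoscope at the time of the procedure". It links the second to a lower infection risk for future patients. Secondary endpoint 3 is the direct measure of that benefit, so it is worth keeping the record free of an avoidable doubt.

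**Working it through.** **Who does what.** The point rests on the text, not on a figure. Set side by side, the documents give:

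| Step | Role named | Stated to be blind? |
|---|---|---|
| Randomises the patient | Research coordinator | No |
| Provides the simethicone and instructions | Research coordinator | No |
| Handles the spreadsheet of regimen codes | Study coordinator and/or assigned research personnel | No |
| Decides whether SIM is used in the procedure | Endoscopist | Yes |
| Records the amount of SIM used | Research coordinator | No |

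The first, second and fifth rows name the same role. That the role knows the arm is inferred from the first two tasks; the documents do not say so outright. They also do not say whether the study coordinator and the research coordinator are the same role, or whether one or several people fill it. No nursing log or other source record is described for this endpoint.

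**The plan's own sample size.** The illustration below uses 150 per arm, so that figure was checked first with the plan's formula. The inputs are the PDR figures of 26.7% and 13.7% in the sample size section. Two-sided alpha 0.05 and beta 0.2 are stated there for the preparation-scale calculation and assumed to carry over.

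- Mean p = (0.267 + 0.137)/2 = 0.202, so pq = 0.202 × 0.798 = 0.1612.
- n = 2 × (1.960 + 0.842)² × 0.1612 / (0.130)² = 149.7, which rounds up to 150 per group, as stated.

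Nothing in this calculation depends on who records SIM use.

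**How much one-sided omission would matter (illustrative).** The documents give no rate of intra-procedure SIM use. The assumptions are: use counted as yes/no; the same true rate in both arms, from 10% to 50%; 150 patients per arm; complete recording in the PEG arm; Chi-square test without continuity correction. The number k is the smallest count of uses missed in the PEG+SIM arm alone that gives p<0.05.

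| Assumed true rate | True uses per arm | k missed | p | k as % of uses | k as % of arm |
|---|---|---|---|---|---|
| 10% | 15 | 9 | 0.0417 | 60.0 | 6.0 |
| 20% | 30 | 13 | 0.0389 | 43.3 | 8.7 |
| 30% | 45 | 15 | 0.0455 | 33.3 | 10.0 |
| 40% | 60 | 17 | 0.0387 | 28.3 | 11.3 |
| 50% | 75 | 17 | 0.0482 | 22.7 | 11.3 |

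Worked example for the first row: 6 recorded uses against 15 gives a pooled proportion of 21/300 = 0.07. Chi-square = (9/150)² / (0.07 × 0.93 × 2/150) = 4.15, above the 5% critical value of 3.84. With continuity correction, k rises by one in each row, for example to 10 of 15 and 18 of 75.

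The table has two limits. The Methods record an amount, which under the Statistical analysis section could be compared by t-test or Mann-Whitney, so the table says nothing about biased amounts. It also starts from no true difference; if a real but non-significant difference existed, fewer missed records would be enough.

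**The case against.** The strongest reply is that the part of this endpoint that needs judgement is already protected. SIM is given when an endoscopist asks for it, and the endoscopists are stated to be blind. The coordinator neither triggers nor judges its use, and an amount is a fairly objective thing to write down. This stands, and it is why the point is minor. It protects the request, however, and not the record.

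A second reply is that different people may fill the coordinator role. This also stands. A reader might infer that the person who hands out the simethicone is the person who records its use in the same patient, but the documents do not show that. They only fail to require separation.

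A third reply is that observer-blinded can fairly describe a design in which the endoscopists, who observe and score, are blind. That is accepted. A reader might see a contradiction between the label and the recording arrangement, but the documents do not establish one.

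Finally, the omission needed in the illustration is large and one-sided, and nothing in the documents suggests that it would happen. That is fair, and the table should not be used to raise the weight of the point.

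**Conclusion.** The point holds as a minor, cheap improvement. As written, one role probably knows the arm and also makes the only described record of secondary endpoint 3. The consequence is confined to possible biased or incomplete recording of one of four secondary endpoints. ADR, which is determined from pathology results, and the sample size do not change.

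The textual overlap of tasks is certain. The coordinator's knowledge of the arm is a role-level inference. The size and direction of any bias cannot be determined from the documents, and the range from 9 of 15 to 17 of 75 missed uses is illustrative only.

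Two stronger readings are not supported. One is that the SIM comparison will be biased; the documents show only that a safeguard is missing. The other is that a coordinator who knows the allocation would unblind the endoscopist and so affect the bubble and preparation scores. The documents do not address that; it is a separate issue and not part of this point.

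**What to change.** In the colonoscopy paragraphs of the Methods, change the sentence that names the recorder. The amount of intra-procedure SIM, including zero, should be recorded at the time it is given by someone already in the procedure team without access to the allocation, for example a procedure nurse. Entering zero separates no use from a missing entry.

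Add two short statements:

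- This recorder is blind to the preparation. The present text only tells patients not to disclose their regimen to the nurses, which does not by itself say that the nurses are blind.
- Staff who know the allocation do not disclose it to the recorder. This concerns the allocation only and does not limit the passing on of safety information.

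The cost is one changed sentence, two added ones and a small recording task for the person named. The documents do not describe nurse workload, so the unit should confirm that the task fits. If a procedure nurse already in the room takes it on, no extra staff are needed. No endpoint, test or sample size changes.

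### The BPS part of the adequacy rule has no segment minimum, so 3-3-1 counts as adequate and 2-2-2 does not; this affects only the adequacy proportion

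*Combined protocol and SAP*

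**What the plan says.** Secondary endpoint 2 asks whether adding SIM gives better colon preparation. Methods has the endoscopist grade the rectosigmoid, transverse and ascending segments on two scales. On the BPS each segment runs from 0 to 3, with 3 best. On the BS, which describes bubbles only, each runs from 0 to 3, with 3 worst. Totals are formed by addition: "The overall BS and BPS scores will be determined by adding the scores of each segment of the colon". Adequacy is then defined: "A total BPS score of >6 and a BS of <2 will be considered adequate preparations". No minimum BPS grade is set for a single segment.

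The Sample size calculation section sizes the BPS outcome on a proportion taken from a cited randomized trial: "99% of patients receiving PEG+SIM had BPS scores of 6-9 compared to only 84% in the patients who received PEG". That gives 55 per arm.

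The Statistical analysis section treats the scores differently: "Interval data (e.g. BPS, BS) will be presented as Median (Q1, Q3) in each group and compared with nonparametric Mann-Whitney". It names no test for adequate versus inadequate. Such a proportion would fall under the general rule: "Categorical data (e.g. ADR) will be described using frequency and proportion (%) in each group and will be compared using Chi-square or Fisher's exact test". Data Collection item 6 lists the BPS score without saying whether the segment grades are entered or only the sum.

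**The concern.** A summed score lets a clean segment offset a dirty one. Visibility is lost locally. Background/Significance says of residual stool, bubbles, bile, fluid and debris: "Any of these features can ultimately lead to missed lesions". A well-prepared rectosigmoid does nothing for what cannot be seen in the ascending colon. With no segment minimum, a patient can be classed as adequately prepared on the BPS while a third of the scored segments has a grade of 1, and a patient with every segment at 2 is classed as inadequate.

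At stake is the meaning of the adequacy proportion in each arm. If SIM lifted a single segment from 1 to 2 or 3 in patients whose other two segments are already at 3, that proportion would not move. The Innovations section says the pilot data will be used to design a full-sized trial, so the definition may be carried forward. If only the sum is entered, the segment information cannot be recovered later.

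**Working it through.** **Inputs.** Three segments, each graded 0-3 on BPS and on BS; adequacy at BPS total >6 and BS <2 (Methods). BPS rates of 99% and 84% at scores 6-9, two-sided alpha 0.05, beta 0.2, 55 per arm for this outcome, 150 per arm in the trial (Sample size calculation).

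**1. The plan's own figure.** Its formula is n = 2(z₁₋α/₂ + z₁₋β)² pq / (p₁ − p₂)². Taking p as the mean of the two rates, p = (0.99 + 0.84)/2 = 0.915, q = 0.085 and pq = 0.077775. Then n = 2 × (1.960 + 0.842)² × 0.077775 / 0.15² = 54.3, rounded up to 55. The stated figure is reproduced. It rests on a total of at least 6, not on >6.

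**2. BPS patterns under the Methods rule (total >6).** There are 4³ = 64 patterns.
- Total 9: 3-3-3, 1 pattern.
- Total 8: 3-3-2 in any order, 3 patterns.
- Total 7: 3-2-2 in any order, 3 patterns; 3-3-1 in any order, 3 patterns.

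So 1 + 3 + 6 = 10 patterns pass, and 3 of them contain a segment below 2. A segment graded 0 can never pass, because 3 + 3 + 0 = 6. The pattern 2-2-2 also totals 6 and fails.

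**3. BPS patterns under the sizing range (total 6-9).** Total 6 adds 10 patterns: 2-2-2 (1), 3-2-1 in any order (6) and 3-3-0 in any order (3). Now 20 pass, and 3 + 6 + 3 = 12 contain a segment graded 0 or 1.

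**4. With a segment minimum of 2.** There are 2³ = 8 patterns with every segment at 2 or 3, and all total at least 6. Combined with >6, 7 pass (2-2-2 is still excluded). Combined with 6-9, all 8 pass. The choice of total therefore decides how 2-2-2 is classed; the segment minimum does not.

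**5. What BS <2 adds.** The sentence does not say whether the limit applies to the BS total or to each segment. As a total, only 0-0-0 and the three patterns with a single 1 pass. Per segment, 8 patterns pass, with totals up to 3. Either way, no segment with BS 2 or 3 can pass. The rule thus protects every segment against bubbles, but not against stool or debris.

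**6. What the planned test sees.** A change from 3-3-1 to 3-3-2 or 3-3-3 moves the total from 7 to 8 or 9. The patient is adequate on BPS before and after, so the proportion does not change, but the ranks in a Mann-Whitney test do.

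An illustration, using rates that are assumed and not found in the documents: two segments always at 3, and the third at 1 in 20% of PEG and 5% of PEG+SIM patients, otherwise 2 or 3. Total >6 gives 100% adequate in both arms. A segment rule gives 80% vs 95%, with power of about 98% at 150 per arm (normal approximation). Simulated Mann-Whitney power on the total in the same scenario is about 71% to 99%, depending on how the remaining grades divide between 2 and 3 (lowest when they divide evenly).

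The counts in steps 2 to 5 are of patterns, not patients.

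**The case against.** The strongest reply is that the planned between-arm analysis of BPS is Mann-Whitney on the scores, so a gain in one segment is retained and no conclusion on secondary endpoint 2 need rest on the dichotomy. That stands. It confines the point to the adequacy proportion, which the plan defines and whose counterpart it uses for sizing.

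Second, SIM acts on bubbles, and BS <2 already bars any segment with heavy bubbles. What slips through is a segment graded BPS 1 with few bubbles, which is poor mainly for reasons the plan does not expect SIM to change. That also stands, and it makes a hidden SIM effect less likely. It does not make 3-3-1 a sound description of adequate preparation.

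Third, a minimum of 2 has no source in the documents. This is correct: it is a proposal for an endpoint definition, and a sensitivity definition would meet the need.

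A reader might infer three stronger claims that the documents do not support:
- That adequacy is judged on the BPS total alone. The same sentence also requires BS <2.
- That the trial would miss a real benefit in the worst segment. The score-based test would usually detect it, even in the assumed scenario built to hide it.
- That 3 in 10 adequate patients would have a poor segment. The count is of patterns, and no segment-level rates are given.

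**Conclusion.** The point holds in a limited form. The BPS condition has no segment minimum, so 3-3-1 passes and 2-2-2 does not, and the BS condition does not make up for this where the cause is stool or debris. Under >6 the masking is limited to one exact pattern: one segment at 1 with both others at 3. It would be wider under the 6-9 range used for sizing (12 of 20 patterns, including 3-3-0), but that range is a cited trial's reporting category, not this plan's adequacy rule.

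The consequence is confined to the adequacy proportion within one of four secondary endpoints. The ADR analysis and the Mann-Whitney comparison of BPS totals are untouched. The size in patients is unknown, because the documents give no segment-level rates. The conclusion assumes that an adequacy proportion will be reported by arm, which the plan implies by defining adequacy but does not state. This is a minor point, worth acting on because the change is cheap and unrecorded segment grades would be lost.

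**What to change.** - In Data Collection item 6, enter the three segment BPS grades as well as the total.
- In Methods, prespecify a BPS adequacy definition that requires no segment below 2 in addition to the total, as the main definition or at least as a sensitivity definition.
- In Statistical analysis, state that this proportion will be compared between arms by chi-square or Fisher's exact test, and keep Mann-Whitney on the BPS total.
- Reconcile the >6 cut in Methods with the 6-9 range in the Sample size calculation. This also settles how 2-2-2 is classed, which the segment minimum alone does not do while >6 is kept.
- State whether BS <2 applies to the total or to each segment.

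**Cost.** A few sentences and up to three data fields. The segments are already graded, so no new assessment is needed. The downside is a somewhat lower adequacy rate that is less directly comparable with the published 99% and 84%. Using the segment minimum only as a sensitivity definition avoids most of that.
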